CC-P&BM currently has a wait-list of over 300 adults referred for mental health evaluation and treatment. Access to psychiatric clinicians remains insufficient despite increasing numbers of providers in our clinic and the mental health needs associated with the pandemic are rising. As a result, a clinical intake coordinator (Licensed Professional Counselor) began in the CC-P&BM ambulatory clinic September 2021. This coordinator will individually contact people on the wait-list for psychiatric care by phone as part of routine care, beginning with the referrals most remote in time. The coordinator will complete an intake assessment for each wait-list individual who wants a psychiatric referral. Prior to the initial intake assessment by the intake coordinator, wait-list individuals will receive a bundle of PROMs automatically (through Owl Insights) to complete. These measures include the PHQ-9, GAD-7, BASE-6, DAST-10, USAUDIT, Covid Event Checklist and the Adult Behavioral Health Screen (ABHS), all of which are currently used in routine ambulatory care. The intake coordinator will complete the intake assessment, noting the completion, and scores of, the PROMs. Scores of the PHQ-9, GAD-7 and BASE-6 will be utilized to triage the most severe referrals and move them up for a sooner appointment (the triage system of scores and Nurse-Practitioner vs Medical Doctor screening questions are attached to this application). Any concern about patient safety is also addressed immediately during this intake and is also noted in the materials attached to this application. **Up to this point, all intake coordinator/referral interaction are part of routine care.**

If eligible and capable of consent based on intake coordinator clinical judgement, individuals will then be randomized to participate to the no intervention group (completion of screening PROMs only during the intake coordinator assessment) or the minimal intervention group (intake coordinator assessment, including PROM screening and then prospective monthly PROM completion in addition to assigned microlearning

patient education videos). We will analyze changes in PROM scores for individuals engaged in both wait-list groups and compare results to their PROM scores at the initial provider telemedicine visit and over time (6 months post first provider assessment). Consent may be in-person with hard copy consent forms and signatures or through e-Consent either in-person using ipads or remotely using REDCap.

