10.6 State the research hypothesis or the question that the research will answer.

List the research objectives and expected outcomes. A primary outcome or objective must be identified. After the statement of the primary objective, secondary objectives may be listed. Objectives should be simple and specific.

Aim 1 will use PROMs to assess the symptomology and well-being of adult individuals on a wait-list group referred to CC-P&BM clinic from their initial referral to their initial psychiatric session.

In particular, we propose randomizing wait-list individuals to one of two groups to assess the influence of time alone awaiting initial psychiatric clinician assessment (no intervention) versus minimal intervention using prospective monthly repeated PROMs and viewing microlearning patient education videos while awaiting initial psychiatric clinician assessment.

Aim 2 will use PROMs to determine whether there is a difference in clinical symptomology and well-being for patients during telemedicine treatment with their practitioner compared to wait-list individuals.

10.7 State how qualitative and/or quantitative data will be analyzed in order to answer the research questions.

Include an analysis from a statistician (or someone familiar with statistical methods) that either indicates the power calculation for the sample size necessary to meet the primary study outcome or objective OR a statement from the statistician indicating reasons why a power calculation is waived or not necessary for this study. Also include the statistical test(s) that will be used to analyze your primary study objective (t-test, chi-square, etc.). Secondary outcomes may be listed as descriptive.

If this is a proof of concept or feasibility study that includes limited efficacy testing, please provide a description on how your design will determine if an intervention should be recommended for broader efficacy testing. If a study is meant to be solely descriptive, then the primary outcome or objective must be limited in scope. As such, the study results apply only to the sample being studied, and conclusions cannot be drawn about the larger population.

This is required for ALL studies, as this section helps the IRB confirm the data being collected are relevant to the study aims and planned analysis.

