The primary outcome of interest is the change in total PROM score for each assessment required of patients enrolled in the study. Initial PROM scores will be acquired and assessed after referral into the CC-P&BM program. The potential to receive few records per patient is believed to be relatively high; therefore, the final PROMs completed for each assessment will be used to determine the change in total score. This change will be compared between patients receiving telemedicine and those of the control (wait-list) groups. A two-sample t-test or non-parametric equivalent of the mean change in total PROM will be performed to determine if the change is significantly different among treatment types. An alpha of 0.05 will be used to assess statistical significance. Univariate and multivariate analyses may occur to measure numeric variables by measures of central tendency and variation and categorical variables by frequencies and percentages. Trends of PROM scores will be evaluated between treatment types by the time in program.

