2. Randomly assign patient into group (REDCap will do this when you start a new patient record); inform patient of the group they have been randomly assigned into to provide further instructions.
3. Provide all patients with CONNECT phone number at termination of the call.

Initial consenting process occurs after routine clinical psychiatry intake assessment by intake coordinator (if intake coordinator assesses that patient has capacity to pursue study discussion): 30-45 min consent process through REDCap or hard copy in-person. REDCap will be utilized to perform randomization. There is no blinding due to the nature of the wait-list control groups; both patients and investigators will be aware of study group assignment.

No intervention group randomization: no additional time/study procedures occur after consent; **SO C monthly PROMs DO NOT begin until after initial psychiatric provider evaluation for 6 additional months.**

Minimal intervention randomization: each month PROMs including PHQ-9, GAD-7 and BASE-6 are sent automatically for subject to complete via email or cell phone before initial psychiatric provider appointment - takes approximately 15 minutes to complete; watching microlearning videos about illness/symptoms takes approximately 15-30 minutes to watch depending on # videos recommended. Current wait-time for patients to see MD provider is 3-4 months; therefore, subjects in the minimal intervention group will participate in the study for up to 6 months before beginning regular treatment with provider.

PROM data from both groups will continue at initial psychiatric provider evaluation and monthly as is current clinical practice. Therefore, an additional 6 months of PROM data for each group will be followed to assess the research question of whether a no intervention or minimal intervention group may provide benefits to patients waiting to be seen and followed by psychiatric providers.

Total study participation time = 6-12 months depending on length of wait time before first psychiatric provider appointment

You must attach surveys, instruments, interview questions, focus group questions, etc. in the Initial Submission Packet and label them clearly.

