If this research includes risks that might require immediate or prompt medical management, describe access to/availability of emergency medical equipment and trained personnel at each setting where procedures that impart physical/health risks will take place. If this information is available in the study protocol indicate the page numbers where the information can be located.

Please see section 20.1 and 20.2

23.4 For studies involving drugs, devices, biologics, or imaging, describe the type of pregnancy testing that will occur and how frequently it will be conducted on women of reproductive potential.

Include:

- **If pregnancy testing will not be conducted, provide the reason.**
- **State the types of birth control methods women of reproductive potential will be instructed to use.**
- **If women will not be instructed about acceptable methods of birth control, provide the reasoning.**
- **Describe the birth control methods men of reproductive potential will be instructed to use. If men will not be instructed about acceptable methods of birth control, provide the reasoning.**

NA

23.5 Does the research include screening tools, questionnaires, or procedures that may indicate the presence of serious depression and/or suicidal ideation?

Yes No

Describe the criteria that will be used in the screening tools/questionnaires to determine if the participant is considered to be at risk. Describe or upload the plan to refer or intervene in the event that potential serious depression and/or suicidal ideation are identified.

Tiered Levels of Severity of PROMs:

Tier 1: (severe) PHQ-9 = 21-27, or GAD-7 =17-21, or Suicidal Ideation (Q9 >0)

Tier 2: (moderate) PHQ-9 = 16-20, or GAD-7 = 11-15

Tier 3: (mild) PHQ-9 =11-15 or GAD-7 = 6-10

PHQ-9 <11, GAD < 6 (normal to minimally ill)

Tier 1 severe - patient will be put at the top of the referral list for sooner appointment time (if currently safe), otherwise crisis intervention occurs as below.

If patient answers "yes" to question 9 (ie >0) on the PHQ-9, or reports suicidal ideation, ask follow-up questions regarding this: provide number to CONNECT, offer number to the National Suicide Hotline, complete a wellness check if necessary.

1. National Suicide [contact]
2. CONNECT: [contact]
3. Roanoke County Wellness Check: [contact]
4. Roanoke City Wellness Check: [contact]
5. Emergency/Actively Suicidal: 911

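### Intake severity sets how long a participant waits, so a wait-list trend of raw scores over time can fall by selection alone, and the number of monthly intervention rounds varies with severity

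*Combined protocol and SAP*

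**What the plan says.** - **Triage (10.5, 23.5).** PHQ-9, GAD-7 and BASE-6 are completed before the intake assessment and are "utilized to triage the most severe referrals and move them up for a sooner appointment". Section 23.5 defines Tier 1 as PHQ-9 21-27, GAD-7 17-21, or any non-zero answer to PHQ-9 item 9, and adds: "Tier 1 severe - patient will be put at the top of the referral list for sooner appointment time". No wait is given for any tier. All of this happens before consent and randomisation.
- **Wait and intervention (19.1).** "Current wait-time for patients to see MD provider is 3-4 months". In the minimal-intervention arm, "each month PROMs including PHQ-9, GAD-7 and BASE-6 are sent automatically for subject to complete via email or cell phone before initial psychiatric provider appointment"; microlearning videos are also assigned. The no-intervention arm has no study measures between intake and the first provider evaluation. After that visit both arms complete monthly PROMs for six more months. REDCap randomises, and no stratification factor is named.
- **Aims (10.6).** Aim 1 covers the period from referral to the first psychiatric session, with the no-intervention arm meant to show what the passage of time does by itself. Aim 2 compares patients in telemedicine with wait-list individuals.
- **Analysis (10.7).** The primary outcome is change from the initial to the final completed PROM, compared by a two-sample t-test or non-parametric equivalent at alpha 0.05. No term for tier, baseline score or wait length appears. The section then adds: "Trends of PROM scores will be evaluated between treatment types by the time in program".

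**The concern.** The scores that form the baseline also decide when a participant stops being a wait-list participant. Aim 1 closes at the first session, and 10.7 contrasts treatment types, so the natural reading is that a participant's data move from the wait-list series to the telemedicine series at the first appointment. Triage sets that moment. Section 10.7 says change for the primary outcome but only scores for the trend, and nothing says the trend is within person.

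On that reading, the average among those still waiting drops as the sickest are called in, and the telemedicine average starts high for the same reason. Improvement with waiting, and the gap between wait-list and telemedicine at a given time, would partly reflect the triage rule. Aim 2 is the more exposed, because that comparison is not between randomised groups.

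For Aim 1 the issue is different. The intervention runs only until the first appointment, so early-seen participants can receive few monthly rounds or none, which would shrink the contrast between arms.

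**Working it through.** The documents give no power calculation, effect size or SD, so there is no planned figure to reproduce. Everything below is illustration.

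**1. Why the mean falls.** Let Tier 1 have share p and intake mean m1, the others m0, and everyone M = p·m1 + (1-p)·m0. Once Tier 1 has left, the waiting mean differs from M by m0 - M = -p(m1 - m0), with no change in anyone.

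Assumed for the simulation: underlying PHQ-9 mean 14, SD 6, measurement SD 2.5, range 0-27; Tier 1 by PHQ-9 only; Tier 1 seen at 0.5 months, others at 3.5; waits vary by ±25%. Result: p = 0.16, M = 13.99. Those still waiting at month 1 average 12.46, having risen 0.28 from their own intake, so m0 = 12.46 - 0.28 = 12.18. Then m1 = (13.99 - 0.84 × 12.18)/0.16 = 23.49, and -0.16 × (23.49 - 12.18) = -1.81. Selection contributes -1.81 and regression to the mean +0.28, a net fall of 1.53.

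**2. Range of assumptions** (400,000 simulated participants per scenario, no true change):

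| Scenario (waits in months) | Tier 1 share | Mean at intake | Mean of those waiting at month 4 | Raw slope/month | Within-person slope/month |
|---|---|---|---|---|---|
| No triage, all 3.5 | 15.8% | 13.97 | 13.96 | 0.00 | 0.00 |
| Tier 1 at 0.5, others 3.5 | 16.0% | 13.99 | 12.45 | -0.43 | +0.07 |
| Tier 1 at 1 | 15.8% | 13.98 | 12.49 | -0.49 | +0.07 |
| Tier 1 at 2 | 15.9% | 13.99 | 12.46 | -0.48 | +0.03 |
| Tier 1 at 0.5, item 9 also counted (assumed frequency) | 33.9% | 13.98 | 11.48 | -0.75 | +0.13 |
| Graded by tier: 1/2/3/4 | 15.9% | 13.99 | 7.63 | -1.51 | +0.13 |
| Tier 1 at 1, mean 12 | 9.6% | 12.07 | 11.09 | -0.32 | +0.04 |
| Tier 1 at 1, mean 16 | 24.5% | 15.89 | 13.76 | -0.71 | +0.09 |

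With the whole cohort followed past the appointment, the mean stays flat in every scenario (13.97 to 13.99 over months 0-4 with Tier 1 seen at 2 months).

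**3. Control arm.** Controls have no monthly series, but they repeat the measures at an appointment whose date triage sets. A separate run with no true change assumed PHQ-9 mean 13-16, SD 5.5-6, measurement SD 2.5; GAD-7 mean 11.5, SD 5; correlation 0.7; tiers on scores only. The second PHQ-9 averaged about 18-21 in early-seen Tier 1 and 12-14 in the rest. Plotted against time in program, that looks like improvement with waiting.

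**4. Rounds received.** Tier 1 gets 0 monthly rounds at a 0.5-month wait, 0.5 on average at 1 month (half get none), and 1.5 at 2 months. Other tiers get about 3, or 2.6 with graded waits.

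**5. Dilution in Aim 1.** If a fraction f of the minimal arm gets no effect, d becomes d(1 - f), and power is about Φ(d(1 - f)√(n/2) - 1.96). Take n = 100 per arm: 11.3 states 100 for no intervention, 11.2 states 200 in total, and 100 in the minimal arm is inferred. For an assumed d = 0.4:

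- f = 0: 0.40 × 7.071 - 1.96 = 0.868, power 81%
- f = 0.1: d = 0.36, power 72%
- f = 0.2: 0.32 × 7.071 - 1.96 = 0.303, power 62%
- f = 0.3: d = 0.28, power 51%
- f = 0.4: d = 0.24, power 40%

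**6. Randomised contrast.** With the same triage in both arms and no true effect, the simulated difference between arms in change at the first visit was -0.013 points, effectively zero.

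**The case against.** The strongest reply is that the plan never says it will plot raw means among those still waiting. Time in program is undefined, the primary outcome is already change within a person, 10.5 speaks of changes in individuals' scores, and nobody leaves the data at the appointment, since 19.1 and 19.4 keep both arms under monthly measurement for six more months. If the trend spans both phases, or uses within-person change, the artefact disappears or becomes negligible. All of that stands, and it is why the point is conditional. It does not dispose of the point, because the six months of follow-up keep people in the study but not in the wait-list category that Aim 1 and the trend comparison describe.

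It can also be said that controls, the arm meant to show time alone, have no monthly series from which the sickest could drop out. That is correct. Their single repeat measure is nevertheless taken at a time that severity determines.

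Three further points stand. The videos are part of the minimal intervention, and nothing says they wait for the first monthly send, so an early-seen participant may still receive something. The score distributions, tier shares and waits are assumed, and the triage attachment that might give Tier 1 waits is not among the documents. Finally, consent began on 4.6.22 (13.3) and the form is dated 03/16/2023, so changing the randomisation may reach few participants.

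**Conclusion.** The point holds in conditional form. Wait length depends on intake severity by design, and 10.7 has no safeguard. If trends use raw scores switched from wait-list to telemedicine at the first appointment, selection alone gave slopes of about -0.3 to -1.5 PHQ-9 points a month on the assumed inputs; within-person slopes were at most +0.15. Aim 2 is affected most.

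Four stronger readings are tempting, and the documents do not support them:

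- **That the planned trends will fall by selection.** This needs both raw scores and a waiting-phase series; 10.7 leaves both open.
- **That triage biases the randomised comparison.** Intake triage precedes randomisation and acts alike on both arms. Section 15.18 does describe monthly severity and safety assessment in the minimal arm only, but nothing says that a monthly score moves an appointment, and the script in 19.1 says participation does not affect the wait.
- **That Tier 1 receives none of the intervention.** No Tier 1 wait is stated, and videos may still be assigned. Dilution is possible, but its size is unknown.
- **That regression to the mean flatters telemedicine.** This depends on whether intake or the first visit is the treatment baseline, which 10.7 does not say. The Tier 1 fall on retest is modest in any case: about 0.5-0.9 points when either score can qualify. With PHQ-9 alone it is about 1.5: the retest mean is (13.99 - 0.84 × 12.46)/0.16 = 22.02, against 23.49 at intake.

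**What to change.** Leave the triage rule as it is. In 10.7:

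- Define time zero, and label each PROM as waiting phase or treatment phase.
- Analyse trends as within-person change from intake, for example in a participant-level longitudinal model, with intake tier or baseline score as a covariate.
- Adjust the Aim 1 and Aim 2 comparisons for intake severity.
- Report wait length and monthly sends received, by tier and arm. This will show how much dilution there was.

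If enrolment is still open, stratify the REDCap randomisation by Tier 1 versus others, which is known before randomisation. Otherwise stratify in the analysis, which also covers those already randomised.

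Before tier is used as a covariate, two passages need reconciling: 10.5 lists BASE-6 among the triage scores but the tiers in 23.5 do not use it, and a GAD-7 score of 16 falls in no tier.

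The cost is analysis-plan wording, slightly more analysis work and possibly one REDCap setting. No new data are needed, because the intake scores are already collected. Tier-specific estimates will be imprecise at about 100 per arm and should be treated as descriptive.

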Data collection will be entered into REDCap by [name] (Psychiatry Intake Coordinator) and reviewed by the PI or sub-investigator. [name], a VT Psychology graduate student, will be the data manager for the project. Thus, we request that she have access to REDCap data, without PHI access.

Data in REDCap that would be visible to [name] at VT would be:

subject number
randomized group (no intervention or minimal intervention)
date of assessment by [name] will be put as day 1 NOT a specific date of appointment
PHQ-9, GAD-7, BASE-6, USAUDIT, DAST-10 scores

Covid Event Checklist (positively checked answers with respect to COVID infection, prevention, negative mental health effects of Covid, SDOH and resiliency factors) - there are no dates or identifying information in this checklist, simply the check-marked items themselves
Adult Behavioral Health Screen (ABHS) (marked as completed or not)

The VT collaborator would not have access to any of the 18 HIPAA identifiers.

Data from REDCap will be exported to SPARC by HART and de-identified to allow other non-Carilion study members ([name]) to analyze data that is de-identified.

10.0

Human Subjects Research Description

10.1 In the opinion of the Principal Investigator, does this research impart minimal risk or greater than minimal risk to subjects?

As defined by regulation, minimal risk means that the probability and magnitude of harm or discomfort anticipated in the research are not greater in and of themselves than those ordinarily encountered in daily life or during the performance of routine physical or psychological examinations or tests. Please note that the IRB makes the final determination of risk level and may ask you to change this based on their decision.

If this is a Conversion of a Paper Application, select the risk level that has been determined already by the IRB at most recent review per the most recent approval letter (expedited review = minimal risk, full board review = greater than minimal risk).

- Minimal Risk
- Greater than minimal

10.3 Select ALL the types of research activities that will be involved in your human subject research subject, or select None.

- Drugs, biologics or other FDA-regulated products (other than devices)
- Medical devices
- Review of data/records (i.e. prospective clinical data collection from medical records, reviewing previously collected data)
- Biospecimen collection (i.e. blood, tissue, urine, saliva)

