As of July 2021, **32 Carilion psychiatric clinicians** are engaged in Owl Insights, an MBC vendor. Approximately **500 unique individuals complete monthly PROMs** through this system as part of routine clinical care. Our research group recently conducted analyses of nearly 900 ambulatory adult psychiatric patients in ambulatory psychiatry at Carilion Clinic (CC&PBM) engaging in PROMs via telepsychiatry and in-person modalities. PROM results of a patient cohort in clinical care prior to the onset of COVID-19 (November 2019) through March 2021 demonstrated that depression, anxiety and psychological functioning did not decline as hypothesized but statistically improved (Kablunger, et al., 2021). Data also show that the **engagement rates range from 33 to 74% depending on demographic factors**, and completion rates were significantly different for diagnostic group and payor status of the patient (Kablunger, et. al, 2021). The standard goal for MBC utilization is 80%, while the department goal is to have **all** patients participate in PROM completion. Our research group has also completed focus groups of psychiatric clinicians and staff with regards to Owl Insights and PROMs within the past year, identifying barriers and facilitators to its use and plan training implementation for improved adherence and satisfaction (summary of focus group data and training outline- included in grant application, IRB approved protocol 20-1065). Since March 2020, CC-P&BM has been engaging with patients via telephone and several telehealth platforms. Currently, ambulatory psychiatry uses AmWell, a telehealth platform that provides secure telemedicine visits between clinician and patient. The department has documented between **2100-2300 adult telemedicine sessions monthly and 200-700 in-person visits per month** between June 2020 and June 2021.

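### PROM completion in this clinic varied by diagnosis, payor and demographics, but the only named test ignores these factors, so the contrast is biased if completion patterns differ between the compared groups

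*Combined protocol and SAP*

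**What the plan says.** Section 10.7 expects sparse follow-up: "The potential to receive few records per patient is believed to be relatively high". Its response is that "the final PROMs completed for each assessment will be used to determine the change in total score". The comparison it describes is telemedicine against the wait-list groups, and the method is given in one sentence: "A two-sample t-test or non-parametric equivalent of the mean change in total PROM will be performed". On the error rate it adds: "An alpha of 0.05 will be used to assess statistical significance".

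Section 10.7 names no covariate, analysis set, rule for a participant without a later PROM, or missing-data sensitivity analysis. It allows optional univariate and multivariate work, but describes this as summary statistics. It also promises a look at trends over time, for which it gives no model.

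Section 10.5 (background) shows that completion is not haphazard. In the group's earlier analysis of nearly 900 adult patients at this clinic, "engagement rates range from 33 to 74% depending on demographic factors". The same section gives a second finding, on who fills in the scales: "completion rates were significantly different for diagnostic group and payor status of the patient".

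Section 19.1 sets the measurement schedule. The minimal intervention arm is sent PROMs every month during the wait. The no intervention arm is not sent them until the first provider evaluation. From that visit on, both arms are measured monthly for six months.

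**The concern.** A change score needs two scores. With no other rule stated, the natural reading is that the test runs on participants who have a later PROM. The sponsor's own data suggest who those participants will be, yet the plan makes no use of that information.

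The stake is the contrast itself. If the mix of diagnoses, payors and demographic groups among completers differs between the compared groups, and those factors also predict how scores change, an unadjusted test reads the difference in mix as a treatment effect. There are two ways this can arise:

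- **Between the randomised arms.** During the wait, a participant in the minimal intervention arm can supply a later PROM every month. A participant in the no intervention arm cannot supply one until the first provider visit. Someone who never reaches that visit may therefore be analysable in one arm and not in the other.
- **Telemedicine against wait-list.** This is the comparison that section 10.7 names, and it is not randomised. Nothing in the design balances diagnosis or payor across it, before or after loss of records.

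**Working it through.** The plan states no effect size, standard deviation, power or dropout rate, so it has no figure to reproduce. What follows illustrates how large the bias could be.

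**Inputs from the documents.** Engagement of 33% and 74%, the ends of the range in section 10.5. Enrolment of 200 (section 11.2) with 100 in the no intervention arm (section 11.3), so 100 in the other arm is inferred. Alpha 0.05 (section 10.7), taken as two-sided because the section does not say.

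**Assumptions.** Two strata of equal size, one completing at 74% and the other at 33%. A difference D in mean change between the strata. No true treatment effect.

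**Step 1: the mix among completers.** Share of the high-completing stratum among those analysed = (0.5 × 0.74) / (0.5 × 0.74 + 0.5 × 0.33) = 0.370 / 0.535 = 0.692. Among those enrolled it is 0.500, so the shift is 0.192.

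**Step 2: bias in the unadjusted contrast.** Bias = (share in group 1 − share in group 2) × D.

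| Completion pattern | Difference in share | Bias | For D = 2 to 5 PHQ-9 points (assumed) |
|---|---|---|---|
| Same in both groups | 0.692 − 0.692 = 0 | 0 | 0 |
| In one group only | 0.692 − 0.500 = 0.192 | 0.19 D | 0.38 to 0.96 |
| Opposite in the two groups | 0.692 − 0.308 = 0.383 (before rounding) | 0.38 D | 0.77 to 1.92 |

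**Step 3: effect on the test.** Simulation with 100 enrolled per group, no true effect, 4,000 runs, t-test on completers with and without the stratum as a covariate. D is in within-stratum SD. In the one-group case the other group completes at 53.5% in both strata.

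| D | Pattern | Bias, unadjusted (SD) | Type I error, unadjusted | Type I error, adjusted |
|---|---|---|---|---|
| 0.5 | Same | 0.00 | 5.1% | 5.0% |
| 0.5 | One group | 0.10 | 8.2% | 5.7% |
| 0.5 | Opposite | 0.19 | 16.0% | 5.0% |
| 0.8 | Same | −0.01 | 4.8% | 4.4% |
| 0.8 | One group | 0.15 | 10.8% | 4.6% |
| 0.8 | Opposite | 0.30 | 30.7% | 4.9% |

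Adjusted bias was within 0.01 SD of zero throughout. That is expected, because in the simulation completion depends on group and stratum only.

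**Step 4: when the effect is not uniform.** Suppose the true effect is 0.5 SD in the high-completing stratum and 0 in the other. Over all enrolled it is 0.5 × 0.5 = 0.25 SD. Among completers with matching patterns it is 0.692 × 0.5 = 0.35 SD. This is why zero bias needs a uniform effect as well as matching patterns. A stratum main effect alone would not correct it.

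**The case against.** The strongest case on the other side is that selection into the analysed set does not by itself bias a comparison of two groups. The first row of each table shows this. Section 10.5 reports nothing by study arm, so a difference in pattern is a risk and not an observation. This stands, and it limits the point.

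The difference in prompting is also confined to the wait. Both arms are measured from the first provider visit onward, and one later PROM is enough for a change score. That narrows the mechanism in the randomised contrast without removing it, and does not touch the telemedicine comparison.

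Three stronger readings are tempting, and the documents do not support them.

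- A reader might infer that 33% to 74% of the 200 enrolled will be analysable. The source is "Our research group recently conducted analyses of nearly 900 ambulatory adult psychiatric patients in ambulatory psychiatry", that is, patients already in care, and the figures are the ends of a range across demographic subgroups. They are not the chance that a consented participant returns one later PROM. Sections 11.5 and 22.5 also require that participants can complete PROMs remotely. Nor does section 10.5 give rates by diagnosis or payor.
- A reader might infer from section 9.15 that diagnosis and payor are not collected, since the list there runs to items such as "PHQ-9, GAD-7, BASE-6, USAUDIT, DAST-10 scores" without them. That list is what one external data manager may see. Section 19.1 has demographics entered in REDCap, section 20.1 adds elements from the medical record, and the data collection sheet is an attachment not available here.
- A reader might infer that the test is valid only if completion is unrelated to outcome. That is too strong for a contrast, as the matching-pattern case shows.

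Finally, a change now comes late. Consented enrolment dates from 4.6.22 (section 13.3), the form is dated 03/16/2023 (section 25.1), the study is unblinded (section 19.1), and data trends are reviewed weekly (section 9.11). This stands as a reason for full disclosure of timing.

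**Conclusion.** The point holds as a risk that the plan leaves unguarded. The documents name factors related to PROM completion, expect few records, and specify only an unadjusted test that in effect uses those with a later PROM. The optional summaries and the unmodelled trend evaluation do not fill the gap. The comparison of participants with non-participants in section 22.6 does not cover enrolled patients who stop completing.

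On size, bias runs from zero with matching patterns and a uniform effect, through about 0.19 D, to about 0.38 D with opposite patterns. The two equal strata, their 74% and 33% completion, the value of D and the arm-specific patterns are all assumptions. The documents show neither the direction nor the actual size of any bias. Carrying the clinic's earlier completion data over to wait-list patients is itself an extrapolation.

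This is an improvement that should be made at modest cost. It does not show that the planned result would be wrong.

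**What to change.** Amend section 10.7 as follows:

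1. State the analysis set and how participants without a later PROM are handled.
2. Make the main analysis a likelihood-based mixed model on all completed PROMs, adjusted for the intake score, diagnostic group, payor and the demographic predictors of completion. Multiple imputation using the same variables is an acceptable alternative. If the effect may vary by these factors, include the interaction and average over the enrolled mix, or impute separately by group.
3. Keep the two-sample t-test as a sensitivity analysis.
4. Report completion by arm, overall and within each predictor.
5. Confirm that diagnosis and payor are taken from the medical record into REDCap and carried into the de-identified export.
6. Date the amendment and state that it was made after enrolment began in an unblinded study.

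The cost is an amendment, possibly a few coded fields, and somewhat more data and analysis work. No extra patients or visits are needed. The limit is that adjustment helps only as far as these factors explain who has missing scores. Loss that depends on the unseen score itself would remain.
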